### **3.2 Sample Size**

Approximately 40 subjects will be enrolled in phase 1b of the study, with about 30 subjects in the dose escalation cohorts and approximately 10 subjects in the optional dose expansion cohort. The total sample size may be higher than 40 subjects if, following a DLRM recommendation or Amgen decision to evaluate additional doses, dosing cohorts are added and/or existing cohorts are expanded; or subjects are replaced. Additional subjects may be enrolled in each cohort to enable all screened eligible subjects to participate in the study.

With 40 subjects receiving efavaleukin alfa, there is an 87% chance of detecting an adverse event with a true incidence rate of 5%. Without the optional dose expansion cohort (ie, with 30 subjects), the chance of detecting an adverse event with a true incidence rate of 5% reduces to 79%.

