10.1 Sample Size Determination

10.1.1 Phase 1b

Approximately 40 subjects are planned to be enrolled in the phase 1b portion of the study. Approximately 30 subjects will be enrolled in dose escalation cohorts and approximately 10 subjects may be enrolled in optional dose expansion cohort. The total sample size may be higher than 40 subjects if, following a DLRM recommendation, additional dosing cohorts are added and/or existing cohorts are expanded; or if subjects are replaced as per Section [5.2.1](#). With 40 subjects receiving efavaleukin alfa, there is an 87% chance of detecting an adverse event with a true incidence rate of 5%. Without optional dose expansion cohort (ie, with 30 subjects), the chance of detecting an adverse event with a true incidence rate of 5% reduces to 79%.

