Five dose levels are planned: [REDACTED] µg every 2 weeks (Q2W) (cohorts 1a), [REDACTED] µg every week (QW) (cohorts 2a), [REDACTED] µg Q2W (cohort 3), [REDACTED] µg QW (cohort 4), and [REDACTED] µg Q2W (cohort 5). Dose levels 1a ([REDACTED] µg Q2W) and 2a ([REDACTED] µg QW) will be enrolled concurrently. Three subjects each will be assigned to cohorts 1a ([REDACTED] µg Q2W) and 2a ([REDACTED] µg QW) alternately (total of 6 subjects). After the last subject completes the DLT evaluation period, a dose level review meeting (DLRM) will occur and if deemed necessary, 3 additional subjects each will be assigned to cohorts 1a and 2a alternately (total of 6 subjects) to gain additional information. After the last subject completes the DLT evaluation period, a DLRM will occur and if dose escalation is deemed appropriate, subjects will be enrolled in cohorts 3 ([REDACTED] µg Q2W) 4 ([REDACTED] µg QW), and 5 ([REDACTED] µg Q2W) as follows: first, 3 subjects will be enrolled in cohorts 3. An internal safety review will be conducted by the Amgen Medical Monitor and Global Safety Officer after the first 3 subjects complete the DLT evaluation period. If concerning safety issues are identified, a DLRM will occur to assess if it is safe to proceed with additional enrollment in cohort 3 and concurrent enrollment in cohort 4. If no concerning safety issues are identified in these first 3 subjects, enrollment of the remaining 3 subjects in cohort 3 will proceed without a DLRM. Concurrently, enrollment of 6 subjects in cohort 4 will begin with alternate assignment of subjects between cohorts 3 and 4 until enrollment of cohort 3

has completed. Enrollment of 6 subjects in cohort 5 will begin after the DLRM for cohort 4 is complete. DLRMs for cohorts 3, 4 and 5 will occur after the last subject in that cohort completes the DLT evaluation period.

[figure not shown]
All planned dose levels for a given cohort may be adjusted at any time based on emerging data. Additional dosing cohorts may be added, removed or substituted at any time based on emerging data and the results of continuous modeling. **As a result of a recommendation from an ad hoc DLRM, Amgen discontinued enrollment to cohort 5 at the planned [REDACTED] mcg Q2W dose. Subjects who were on-going at the time of this decision had their dose reduced to [REDACTED] µg Q2W for their remaining visits.**

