After there is at least 1 DLT observed at any dose level, a Bayesian logistic regression model (BLRM) (Bailey et al, 2009; Neuenschwander et al, 2008) will be used to inform dose escalation and the results of this analysis will be provided to the DLRM. Three toxicity probability intervals (TPI) of DLT will be defined: target TPI (20% to 30%), excessive TPI (30% to 60%) and unacceptable TPI (60% to 100%). Adverse events meeting DLT criteria after week 4 and PD information may also be included in the model, as available. The model will recommend an MTD as the dose with highest probability in the target TPI, but with less than 25% probability in excessive TPI and unacceptable TPI. Lower dose levels, intermediate dose levels or alternative dosing schedules may be considered based on all available information as long as they do not exceed the estimated MTD per the model. In addition, Amgen may add subjects to dose levels below the MTD in order to better characterize PK and PD. After DLT is observed, the BLMR model will be run after each dosing cohort and may be run at any time to continuously update the MTD information. For technical details of BLMR, please refer to [Appendix C](#).

The study has been terminated early and therefore, the optional dose expansion cohort of phase 1b and the phase 2 part of the study is canceled.

The overall study design is described by a study schema in [Figure 1](#). The endpoints are defined in Section [2.1](#).

Figure 1. Study Schema

DLRM = dose level review meeting; EOET = end of extended treatment; PD = pharmacodynamics; PK = pharmacokinetics; TPI = toxicity probability interval; SFU = safety follow-up; EOS = end of study; Q2W = every 2 weeks; QW = every week

a Doses for subsequent cohorts will be determined by results of Bayesian TPI and PK/PD modeling of previous cohorts.

b A DLRM is required for escalation to higher doses but not for allocation of additional subjects to doses equivalent to or lower than previously given that have been deemed tolerable.

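### SAP 3.2 still presents 40 subjects and an 87% detection chance as the plan, although SAP 3.1 cancels the expansion cohort those figures need

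*SAP*

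**What the plan says.** SAP 3.2 (Sample Size) carries over the protocol's enrolment plan: "Approximately 40 subjects will be enrolled in phase 1b of the study, with about 30 subjects in the dose escalation cohorts". A further 10 or so were to come from an optional expansion cohort. It then gives two detection probabilities for an adverse event with a true incidence of 5%. The first is "With 40 subjects receiving efavaleukin alfa, there is an 87% chance of detecting an adverse event with a true incidence rate of 5" per cent. The second, in the next sentence, covers the case of 30 subjects and no expansion cohort: "the chance of detecting an adverse event with a true incidence rate of 5% reduces to 79" per cent. Protocol 10.1.1 has the same pair of figures.

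SAP 3.1 (Study Design) records what happened later. The study was terminated early, and "the optional dose expansion cohort of phase 1b and the phase 2 part of the study is canceled". After an ad hoc dose level review meeting, "Amgen discontinued enrollment to cohort 5" at that cohort's planned dose, and subjects still in the study had their dose reduced. The number enrolled in cohort 5 by then is not given.

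SAP Section 10 (Changes From Protocol-specified Analyses) lists the dropped phase 1b interim analysis and the dropped phase 2 analyses. It does not mention sample size.

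**The concern.** The SAP was revised after the termination decision. Section 1 drops phase 2, Section 3.1 records the cohort 5 decision, and Section 5.3 defines treatment periods specific to cohort 5. Section 3.2 was not brought into line. Its enrolment target and its first detection probability depend on about 10 subjects who, by Section 3.1, will never be enrolled.

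The primary endpoints are safety endpoints (SAP 2.1), there is no statistical hypothesis for phase 1b (SAP 2.2), and the safety summaries are descriptive. Section 3.2 is therefore where a reader of the study report would look to judge how much weight to give to an adverse event not having been seen across the pooled subjects. A reader who takes 87% from that section would think the chance of missing a 5% event is about 13%, when it is larger.

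**Working it through.** **Inputs**
- True incidence of the event: 5% (SAP 3.2).
- N with expansion: about 40. N without: about 30 (SAP 3.2).
- Five dose cohorts of 3 to 6 DLT-evaluable subjects (SAP 3.1). Five cohorts of 6 make 30, which matches the planned escalation total.
- Population: everyone with at least one dose (SAP 6.1), so subjects dosed in cohort 5 count.

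**Formula.** Detecting is read as seeing at least one event among all dosed subjects pooled: P = 1 − (1 − 0.05)^N = 1 − 0.95^N.

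**The plan's own figures**
- N = 40: 1 − 0.95^40 = 87.15%. Stated 87%; reproduces.
- N = 30: 1 − 0.95^30 = 78.54%. Stated 79%; reproduces.

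**Does 87% need the expansion cohort?** Solving 0.95^N = 0.13 gives N = ln 0.13 / ln 0.95 = 39.8. So 87% needs essentially all 40 subjects; 39 would give 86.5%.

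**Effect of cancelling the expansion cohort.** 87.15 − 78.54 = 8.6 points. The chance of missing a 5% event rises from 12.9% to 21.5%.

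**Illustration if cohort 5 also fell short of 6.** Assume 6 subjects in each of the other four cohorts (4 × 6 = 24), 0 to 5 in cohort 5, and nobody added or replaced:

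| N dosed | 1 − 0.95^N | Chance of missing a 5% event |
|---|---|---|
| 40 | 87.2% | 12.9% |
| 30 | 78.5% | 21.5% |
| 29 | 77.4% | 22.6% |
| 27 | 75.0% | 25.0% |
| 25 | 72.3% | 27.7% |
| 24 | 70.8% | 29.2% |

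Compared with the no-expansion figure, the further loss is 78.5 − 77.4 = 1.1 points at N = 29 and 78.5 − 70.8 = 7.7 points at N = 24.

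**Sensitivity to the assumption.** The second three subjects in each of cohorts 1a and 2a were to be added only if judged necessary. With 3 + 3 + 6 + 6 + 0 = 18 subjects, the figure would be 60.3%. In the other direction, added or replacement subjects would raise N. The rows below 30 therefore show how the probability moves with N and do not estimate what was achieved.

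**The case against.** The strongest reply is that nothing in 3.2 is false. Both probabilities are conditional statements, both reproduce, and the no-expansion case stands in the sentence right after the 40-subject one. A careful reader who combines 3.1 with 3.2 arrives at 30 and 79% unaided. No analysis or decision rule uses either number, and the safety tables will show the real denominators. This largely stands and limits the point to one of reporting. It does not dispose of it. The enrolment sentence is an unconditional statement about the future that 3.1 contradicts, 79% is still worded as a contingency, and Section 10 is silent.

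Four stronger readings may tempt a reader, and the documents do not support them.

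- **That 87% is a miscalculation.** It is correct for 40 subjects.
- **That 30 is a ceiling and 79% an upper bound.** SAP 3.2 says about 30 and allows added cohorts, expanded cohorts and extra eligible subjects. SAP 3.2.1 allows replacement after fewer than 4 doses, and a replaced subject who was dosed remains in the safety analysis set.
- **That cohort 5 was lost, or that the study dosed 24 to 29.** Only enrolment at the planned dose stopped. Subjects already dosed stay in the safety set, and the reference to ongoing subjects suggests that cohort 5 contributed some, so 24 is a limiting case under the stated assumption. Nor is it a floor, because cohorts 1a and 2a could have stayed at 3 each.
- **That this is the plan's only quantitative statement on a primary safety endpoint.** DLT incidence is also primary, and Appendix C gives simulated operating characteristics for the dose-escalation model. A detection figure for each dose level would be an optional extra, since the plan makes no claim at that level.

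**Conclusion.** The point holds as an internal inconsistency in the SAP. Section 3.2 gives as current a sample size and a detection probability that rest on a cohort cancelled in Section 3.1, and Section 10 does not correct them. The firm part of the effect is the move from 87% to 79%, which the SAP's own figures show. A shortfall below 30 is possible because enrolment to cohort 5 at its planned dose was discontinued, but its size cannot be established without the actual number dosed. The 71% to 77% range is illustrative and rests on full enrolment of the other four cohorts with no additions or replacements. What is affected is the stated detection probability and the reading of events that were not observed; no planned analysis, analysis set or decision rule changes.

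**What to change.** In SAP 3.2:

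1. Label the 40-subject, 87% statement as the original plan.
2. State that the expansion cohort was cancelled, so that 30 subjects and 79% is the planned no-expansion case.
3. Give the number of subjects actually dosed, with its matching probability 1 − 0.95^N. If that number is not yet final, say that it will be reported with the final analysis. Do not write a ceiling or an assumed range into the SAP as fact.

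In SAP Section 10, add one sentence recording the change in sample size and its reason.

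The cost is about one paragraph of text and a less favourable stated figure. No programming or data collection is affected.

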#### **3.2.1 Replacement of Subjects**

Subjects may be replaced if they receive fewer than 4 doses of efavaleukin alfa prior to discontinuing study participation.

#### **3.2.2 Number of Sites**

Approximately 14 sites in North America, Europe, and Asia will participate in the study. Sites that do not enroll subjects within approximately 3 months of site initiation may be closed.

### **3.3 Adaptive Design**

The adaptive design elements implemented for this study is Bayesian logistic regression model to assist dose escalation.

## **4. Covariates and Subgroups**

### **4.1 Planned Covariates**

No covariates will be used for this study.

### **4.2 Subgroups**

No subgroup analyses will be conducted for this study.

## **5. Definitions**

### **5.1 Basic Definitions**

#### **Investigational Product (IP)**

The term 'investigational product' is used in reference to efavaleukin alfa.

## **Actual Treatment Received**

---

**Actual treatment received is the IP the subject actually received regardless of the dose specified in the protocol for the cohort. In cases where a subject received multiple different efavaleukin alfa doses, the actual treatment received will be based on the highest efavaleukin alfa dose received.**

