### **Planned Treatment Period**

**The time period from study day 1 until end of study or, for cohort 5 subjects, until the day before the first dose of IP at the reduced dose (█ mcg), whichever occurred first.**

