### **Dose Reduction Period**

**For cohort 5 subjects, the time period from the first dose of IP at the reduced dose (█ mcg) until end of study, if applicable.**

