### **Number of days on IP**

Number of days on IP is defined as last dose date – first dose date + 1

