### **Treatment Emergent AE (TEAE)**

A treatment emergent adverse event is any adverse event categorized as adverse events starting on or after first dose of investigational product as determined by "Did event start before first dose of investigational product" equal to "No" or missing on the Events eCRF and up to and including 42 days after the last dose of investigational product excluding events reported after End of Study date on eCRF form, whichever is earlier.

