## **9. Statistical Methods of Analysis**

### **9.1 General Considerations**

Standard descriptive statistics will be provided. All binary endpoints will be summarized using the number and percentage of subjects. All continuous endpoints will be summarized using descriptive statistics including mean, standard deviation, minimum, maximum, and number of non-missing observations (n). Summaries will be provided at all scheduled time-points unless specified otherwise. Data collected at unscheduled visits or time-points will be included in the analysis unless stated otherwise. **All safety and efficacy analyses will be performed using the Safety Analysis Set based on subject's actual treatment received.**

Only critical subject-level data listings will be provided in the clinical study report.

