### **9.6.2                   Adverse Events and Disease-related Events**

The Medical Dictionary for Regulatory Activities (MedDRA) version 25.0 or later will be used to code all adverse events to a system organ class and a preferred term.

The subject incidence of adverse events will be summarized for all treatment-emergent, serious treatment emergent, treatment-related, those leading to withdrawal of investigational product, fatal and of special interest (if applicable). The identification of adverse events of special interest is a continuous process. Events may be identified and documented as the safety profile of the drug. The severity of each adverse event will be graded using CTCAE version 4.03 criteria.

Subject incidence of all treatment-emergent, serious treatment emergent, treatment-related, serious treatment-related, those leading to withdrawal of investigational product or other protocol-required therapies, and fatal adverse events will be tabulated by system organ class and preferred term in descending order of frequency. Treatment emergent, serious, and treatment-related events will also be presented by preferred term and worst severity grade using CTCAE version 4.03 criteria.

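### Cohort 5 safety and exposure data collected after the dose cut are reported under the top dose, and no readable safety section uses the two periods the SAP defines to separate them

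*SAP*

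**What the plan says.** SAP 3.1 records that enrollment at the planned cohort 5 dose was stopped and what happened to those already on it: "Subjects who were on-going at the time of this decision had their dose reduced to" a lower dose given every 2 weeks (amount blacked out) for their remaining visits.

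Four rules then decide how these subjects are reported:

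- **Label (SAP 5.1, Actual Treatment Received).** If a subject had more than one dose, "the actual treatment received will be based on the highest efavaleukin alfa dose received".
- **Where the label applies (SAP 9.1).** "All safety and efficacy analyses will be performed using the Safety Analysis Set based on" the actual treatment received.
- **Adverse event window (SAP 5.5).** It opens at the first dose and runs "up to and including 42 days after the last dose of investigational product", or to the End of Study date if that comes first.
- **Days on product (SAP 5.4).** "Number of days on IP is defined as last dose date" minus first dose date, plus 1.

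SAP 5.3 also defines two cohort 5 periods. The Planned Treatment Period runs from study day 1 to end of study or, "for cohort 5 subjects, until the day before the first dose of IP at the reduced dose", whichever is first. The Dose Reduction Period is "the time period from the first dose of IP at the reduced dose" to end of study.

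**The concern.** The incidence of adverse events is a primary endpoint (SAP 2.1) of a dose-escalation study, and laboratory values, vital signs and weight are reported by dose level. The affected dose is the one at which enrollment was stopped, so a reader will want to know what happened at that dose and what happened after subjects came off it. If the label follows the highest dose and nothing is split at the cut, the tables answer neither question.

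The SAP has the tools to answer both, since it defines periods on either side of the cut. A definition changes nothing until an analysis section calls on it.

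**Working it through.** The plan states no figure that is in dispute. The check is first a reading of the text, then two illustrations of scale.

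**1. Does anything in the safety sections stop at the cut?**

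| SAP section | Output | Split at the cut? |
|---|---|---|
| 9.6.2 | "The subject incidence of adverse events will be summarized for all treatment-emergent" and other event classes, plus worst severity grade | No; the window runs past the cut |
| 9.6.3.1 | Visit summaries, post-baseline extremes, shift to worst grade | No |
| 9.6.4 | Visit summaries and post-baseline extremes by dose level | No |
| 9.6.5 | Weight by visit and dose level | No |
| 9.6.8 | Days on product and total dose | No; days run from first to last dose |

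The readable text of 9.6.1 to 9.6.9 names neither period. The dose reduction mentioned in 9.6.9 concerns systemic corticosteroids. Section 9.6.8 names no grouping, but it falls under the rule in 9.1, and protocol 10.4.2.3.8 plans exposure by dose level. The readable part of the SAP change history lists the two periods among added definitions and lists added summaries separately; none of those is by period.

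**2. Effect on incidence (illustration).** A subject counts once per event term. If the first occurrence starts after the cut, that subject enters the top-dose numerator although the event began at the reduced dose. The change in top-dose incidence per such subject is 1/n:

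- n = 6, the planned cohort 5 size (SAP 3.1): 1/6 = 16.7 points
- n = 4 (assumed): 1/4 = 25.0 points
- n = 2 (assumed): 1/2 = 50.0 points

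The actual n is not stated.

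**3. Effect on exposure (illustration).** Assume dosing every 2 weeks from day 1 through week 50, with no extension. Protocol Table 2-2 puts week 50 at day 351, so days on product = 351 − 1 + 1 = 351, all reported under the top dose. The Planned Treatment Period ends the day before the first reduced dose. With assumed cut times:

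| First reduced dose | Top-dose days | Reduced-dose days | Reduced share of 351 |
|---|---|---|---|
| Week 4 (day 29) | 28 | 351 − 28 = 323 | 92.0% |
| Week 12 (day 85) | 84 | 351 − 84 = 267 | 76.1% |
| Week 26 (day 183) | 182 | 351 − 182 = 169 | 48.1% |

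**The case against.** The best defence is that highest-dose labelling is a deliberate, pre-specified convention, written in the same SAP that records the cut. It is conservative for incidence and worst grade: no event disappears, and any misattribution goes to the higher dose. There is no statistical hypothesis (SAP 2.2), the optional expansion cohort and phase 2 were cancelled, and dose level review meetings worked from subject-level listings and plots. On this view the finding asks only for extra tables.

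Much of that is fair, and it is why the highest-dose column should stay. It does not cover everything. Reporting reduced-dose days as top-dose days is not conservative, and neither is a post-cut visit mean that describes the reduced dose under the top-dose label.

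Other points that stand in part:

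- **Hidden text.** Antibody, pharmacodynamic and efficacy text is blacked out or missing and might use the periods. Those areas are left out of this point. The adverse event, laboratory, vital-sign, weight and exposure sections relied on here are readable in substance.
- **Change history.** It is a fragment and its list of definitions is not exhaustive, so it is only weak support. Output by period may have been intended; it is not stated.
- **Exposure.** Protocol 10.4.2.3.8 could be read as exposure at each dose, and total dose is built from the amounts actually given (SAP 5.4), so the sum is correct even if its label is not. The day count is the clearer problem.
- **Illustrations.** The cut times, the full course to week 50 and the smaller values of n are assumptions. The study ended early, and the documents do not show that any reduced subject reached week 50.

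**Conclusion.** The concern holds and should be fixed. Followed as written, the SAP reports reduced-dose data as top-dose data for a primary safety endpoint and for the supporting laboratory, vital-sign, weight and exposure outputs, and it does not show the reduced-dose experience separately.

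The size cannot be computed, because the number of subjects cut, the time of the cut and the actual cohort size are not given. The figures above show scale under stated assumptions; no upper limit is claimed.

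The reach is limited. It concerns subjects given more than one dose, chiefly cohort 5. Visit summaries before the first cut are unaffected, and a cut after week 4 leaves the dose limiting toxicity endpoint unchanged. The effect is on description and interpretation, with no test or error rate involved.

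**What to change.** In SAP 9.6, keep the highest-dose column and add cohort 5 summaries of treatment-emergent adverse events, laboratory results, vital signs and exposure, split by Planned Treatment Period and Dose Reduction Period. Assign adverse events by start date and measurements by assessment date. Report days on product and total dose within each period.

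The cost is SAP wording and programming: both periods are already defined and dosing dates are collected. There is a modest downside. The same few subjects appear in both periods with unequal follow-up, and some events soon after the cut may carry over from the earlier dose. The retained combined column covers those cases, and a footnote should say so.
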